### 9.1.2 Safety

Dose elimination rules are included to provide guidance for doses with a high probability that the rate of toxicity is greater than the target toxicity rate of 20%. For the purpose of overdose control, doses  $j$  and higher levels will be eliminated from further examination if  $\Pr(p_j \geq 0.20 | \text{data}) > 0.95$  and at least 3 participants have been treated at dose level  $j$ , where  $p_j$  is the true DLT rate of dose level  $j, j=1, \dots, 3$ . This posterior probability is evaluated based on the beta-binomial model  $y_j | p_j \sim \text{binomial}(p_j)$  with  $p_j \sim \text{uniform}(0,1)$ , where  $y_j$  is the number of participants experienced DLT at dose level  $j$ . When the lowest dose is eliminated, the trial will stop for safety. The probability cutoff 0.95 is chosen to be consistent with the common practice that when the target DLT rate  $\leq 1/6$ , a dose with 2/3 participants experienced DLT is eliminated. The

above dose escalation/de-escalation and elimination rule can be equivalently presented in the dose escalation/de-escalation table in Section 9.1.1, which will be used to conduct the trial.

### 9.1.3 Statistical properties

Simulations were run to display the performance of the design of this trial. For each of the 4 scenarios considered, 10,000 simulated trials were run. The following table reports the true DLT rate for each dose level, the percentage of simulated trials selecting each dose level, the percentage of participants treated at each dose level, the average number of participants per trial, and the percentage of trials stopping early due to safety concerns. The results displayed in the table below allow for a maximum sample size of 36 participants with a reduced sample size if a trial ends due to observing 12 participants on a single dose level.

Operating characteristics						
	Dose level -1	Dose level 1	Dose level 2	Dose level 3	Average number of participants	% of trials stopped early
Scenario 1						
True DLT Rate	0.03	0.08	0.12	0.2		
Selection %	2.89	15.7	32.7	48.64	23.7	0.1
% Pts Treated	5.6	27.5	34.1	32.8		
Scenario 2						
True DLT Rate	0.05	0.12	0.2	0.28		
Selection %	7.41	36.52	38.13	17.56	23.7	0.4
% Pts Treated	10.6	37.7	33.7	18		
Scenario 3						
True DLT Rate	0.12	0.2	0.28	0.36		
Selection %	29.55	44.92	18.6	3.43	22.3	3.5
% Pts Treated	25.7	43.7	23	7.6		
Scenario 4						
True DLT Rate	0.2	0.28	0.36	0.44		
Selection %	51.73	27.54	5.17	0.5	19.4	15.1
% Pts Treated	41.3	42	13.7	2.9		

## 9.2 Sample Size/Accrual Rate

The maximum sample size is 36 participants and the trial will stop accruing participants once 12 participants have been treated on a single dose level. The maximum target sample size is based on obtaining sufficient information to assess the study aim of establishing the MTD. Operating characteristics provided in the table in section 9.1.3 indicate that the sample size results in a high rate of simulated trials identifying the target dose level as the MTD across multiple dose-toxicity scenarios, highlighting the ability of study design to achieve the primary aim of determining the MTD.

We anticipate accruing 2 patients per month and therefore expect to complete accrual within 18 months.

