## 6.2 Definition of Dose-Limiting Toxicity

Management and dose modifications associated with the above adverse events are outlined in Section 7.

Dose limiting toxicity (DLT) is defined as the occurrence of any of the following toxicities listed below. The DLT period will be from Cycle 1, Day 1 through the first cycle. To be evaluable for a DLT, at least 66% of the prescribed dose of each drug must be received during cycle 1 (i.e., 2 of 3 doses of entinostat must be received or 66% of prescribed carboplatin, etoposide, or atezolizumab dose must be infused to be considered evaluable if no DLT occurred). If treatment-related adverse events result in <66% of drug doses received, patients will be evaluable for DLTs. Any toxicities attributable to cancer or cancer progression will not be considered DLTs.

DLTs if felt to be possibly, probably, or definitely related to entinostat:

- Less than 66% of entinostat (0 or 1 doses) received during the first cycle due to treatment-related adverse event(s)
- Death in the absence of progressive cancer (Any grade 5 adverse event)
- Any adverse event resulting in discontinuation of carboplatin/etoposide chemotherapy prior to Cycle 2
- Any treatment-related toxicity causing delay of more than 3 weeks from planned cycle 2 day 1
- Any  $\geq$  Grade 3 non-hematologic adverse event (non-laboratory), excluding alopecia, uncontrolled nausea or vomiting. Grade  $\geq 4$  uncontrolled nausea or vomiting should be considered a DLT if it persists  $\geq 72$  hours despite maximal medical management.
- Any  $\geq$  Grade 3 non-hematologic laboratory value if medical intervention is required (not including endocrinopathies requiring hormone replacement) or leads to hospitalization

DLTs regardless of relatedness to entinostat (attribution to any study drug):

- Hematologic events
  - Grade  $\geq 4$  febrile neutropenia
  - Grade 4 neutropenia lasting  $>7$  days
  - Grade 3 thrombocytopenia associated with bleeding requiring transfusion or Grade  $\geq 4$  thrombocytopenia.

Dose escalation will proceed within each cohort of 3 patients according to the following scheme. Dose-limiting toxicity (DLT) is defined above.

Escalation/De-escalation Rule												
Number of patients treated	1	2	3	4	5	6	7	8	9	10	11	12
Escalate if # of DLT $\leq$	0	0	0	0	0	0	1	1	1	1	1	1
Deescalate if # of DLT $\geq$	1	1	1	1	2	2	2	2	3	3	3	3
Eliminate if # of DLT $\geq$	NA	NA	2	3	3	3	4	4	4	5	5	5

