#### 9.1.1 Treatment allocation

Participants will be enrolled and treated in cohorts of size 3. Only DLTs that occur within the first cycle will be used for dose finding. As shown in Figure 2, the BOIN design uses the following rule, optimized to minimize the probability of incorrect dose assignment, to guide dose escalation and de-escalation.

The steps to implement the BOIN design are as follows: 1) Participants in the first cohort are treated at dose level 1; 2) To assign a dose to the next cohort of participants, conduct dose escalation and de-escalation according to the rule displayed in the table below; 3) Repeat step 2 until the maximum sample size of 36 is reached, or stop the trial if the number of participants treated at the current dose reaches 12 and the decision according to the table below is to stay at the current dose.

After the trial is completed, the MTD is determined based on isotonic regression as specified in Liu and Yuan (2015). This computation is implemented by the shiny app “BOIN” available at <http://www.trialdesign.org>. Specifically, the MTD is the dose for which the isotonic estimate of

[figure not shown]
the toxicity rate is closest to the target toxicity rate. If there are ties, the higher dose level will be selected when the isotonic estimate is lower than the target toxicity rate and the lower dose level will be selected when the isotonic estimate is greater than or equal to the target toxicity rate.

At the conclusion of the trial, all available safety data will be reviewed. If a significant number of clinically significant adverse events outside the definition of a DLT occurred at the MTD, the recommended phase 2 dose may be a lower dose level than the MTD. Examples of clinically significant events that would be considered are events similar to DLTs that occurred in later cycles outside the DLT window, treatment discontinuation due to an adverse event attributed to entinostat, or patient withdrawal from the study due to intolerable adverse events.

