When using the table below, the following descriptions for decision types should be considered. “Eliminate” means eliminate the current and higher doses from the trial to prevent treating any future participants at these doses because they are overly toxic. When a dose is eliminated, automatically de-escalate the dose to the next lower level. When the lowest dose is eliminated, stop the trial for safety. In this case, no dose should be selected as the MTD. If none of the actions (i.e., escalation, de-escalation or elimination) is triggered, treat the new participants at the current dose. If the current dose is the lowest dose and the rule indicates dose de-escalation, treat the new participants at the lowest dose unless the number of DLTs reaches the elimination boundary, at which point terminate the trial for safety. If the current dose is the highest dose and the rule indicates dose escalation, treat the new participants at the highest dose.

Escalation/De-escalation Rule												
Number of patients treated	1	2	3	4	5	6	7	8	9	10	11	12
Escalate if # of DLT <=	0	0	0	0	0	0	1	1	1	1	1	1
Deescalate if # of DLT >=	1	1	1	1	2	2	2	2	3	3	3	3
Eliminate if # of DLT >=	NA	NA	2	3	3	3	4	4	4	5	5	5

Figure 2: Study Design

$$* \text{DLT rate} = \frac{\text{Total number of patients who experienced DLT at the current dose}}{\text{Total number of patients treated at the current dose}}$$

Figure 3: Study Design

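### Sections 9.1.1 and 9.2 set different stopping rules at 12 patients per dose, and the operating characteristics that 9.2 cites arise only under 9.1.1, with 'stay' read as the same next dose

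*Combined protocol and SAP*

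**What the plan says.** - Section 9.1.1, in its numbered steps, allows a stop before 36 patients if "the number of participants treated at the current dose reaches 12 and the decision according to the table below is to stay" at that dose.
- Section 9.2 has no such condition: "the trial will stop accruing participants once 12 participants have been treated on a single dose level". It then leans on the simulations: "Operating characteristics provided in the table in section 9.1.3 indicate that the sample size results in" a high rate of correct MTD identification.
- Section 9.1.3 introduces those simulations as allowing "a reduced sample size if a trial ends due to observing 12 participants on a single dose level", again without the condition.
- Section 9.1.1 covers two cases in which the dose cannot move. De-escalation at the lowest dose means remaining there, and for the top: "If the current dose is the highest dose and the rule indicates dose escalation, treat the new participants at the highest dose". If the next higher dose has been eliminated, the plan says only that the team should "eliminate the current and higher doses from the trial to prevent treating any future participants at these doses".
- Section 9.1.2 refers to the "dose escalation/de-escalation table in Section 9.1.1, which will be used to conduct the trial". Section 6.2 prints the same table under the sentence "Dose escalation will proceed within each cohort of 3 patients according to the following scheme". Both copies end at 12 patients.

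**The concern.** The two rules give different instructions in ordinary data. In the printed table, 12 patients at an intermediate dose lead to escalation at 0 or 1 DLT, staying at 2, de-escalation at 3 or 4, and elimination at 5 or more. Only 2/12 is a stay.

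Take this path: level 1 has 1/3 (de-escalate); level -1 has 0/3 (escalate); level 1 reaches 1/6 (stay), then 1/9 (escalate); level 2 has 1/3 (de-escalate); level 1 reaches 1/12. The table now says escalate, and level 2 is not eliminated, since that needs 2/3. Section 9.1.1 enrols another cohort at level 2. Section 9.2 closes accrual at 12 + 3 + 3 = 18 patients.

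The MTD is a primary endpoint. If the rule is settled only after the DLT counts are known, stopping becomes data-dependent. A team that follows 9.2 runs a smaller design than the one whose performance the plan reports. A team that follows 9.1.1 can need decision boundaries that the plan does not print.

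**Working it through.** **Inputs from the plan.** Target 20%; cohorts of 3; start at level 1; maximum 36; isotonic MTD with the stated tie rule (9.1, 9.1.1). Elimination if Pr(p ≥ 0.20 | data) > 0.95 under a uniform prior with at least 3 treated (9.1.2). Four sets of true DLT rates (9.1.3).

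**Assumptions not in the plan.** The BOIN interval is taken as 0.6 and 1.4 times the target, so p1 = 0.12 and p2 = 0.28. The isotonic step uses (y + 0.05)/(n + 0.1).

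**Decision table.**
- λe = ln(0.88/0.80) / ln[0.20×0.88/(0.12×0.80)] = 0.0953/0.6061 = 0.1572
- λd = ln(0.80/0.72) / ln[0.28×0.80/(0.20×0.72)] = 0.1054/0.4418 = 0.2385

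With the 9.1.2 elimination rule, these regenerate every printed cell for n = 1 to 12.

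**Simulation**, 60,000 trials per scenario and rule (10,000 for the row marked †):

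| | Sc. 1 | Sc. 2 | Sc. 3 | Sc. 4 |
|---|---|---|---|---|
| **Average N** | | | | |
| Printed in 9.1.3 | 23.7 | 23.7 | 22.3 | 19.4 |
| 9.1.1, stay = same next dose for any reason | 23.7 | 23.7 | 22.3 | 19.6 |
| 9.1.1, escalation blocked by elimination not a stay | 26.1 | 27.3 | 25.6 | 21.6 |
| 9.1.1, only the table's middle zone is a stay † | 28.25 | 27.72 | 25.92 | 23.02 |
| 9.2, 12 on any dose | 20.5 | 19.7 | 18.3 | 16.6 |
| **20% dose selected (%)** | | | | |
| Printed | 48.64 | 38.13 | 44.92 | 51.73 |
| 9.1.1, same next dose | 48.8 | 38.2 | 44.9 | 52.0 |
| 9.2 | 47.6 | 34.5 | 45.0 | 43.5 |
| **Safety stop (%)** | | | | |
| Printed | 0.1 | 0.4 | 3.5 | 15.1 |
| 9.1.1, same next dose | 0.1 | 0.3 | 3.5 | 14.5 |
| 9.2 | 0.1 | 0.3 | 3.1 | 13.1 |

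The 9.2 rule falls short of the printed average N by 3.2, 4.0, 4.0 and 2.8 patients. The Monte Carlo standard error of a selection rate is about 0.2 points here and 0.5 in the printed table, or √(0.2² + 0.5²) ≈ 0.54 for a difference. The gaps of 3.6 points (Scenario 2) and 8.2 points (Scenario 4) are therefore about 7 and 15 standard errors. The matching rule leaves small residues in Scenario 4: 0.2 patients and 0.6 points of safety stops.

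**Consequences of the 9.2 rule.** In Scenario 4, selection of a dose above the MTD rises from 27.54 + 5.17 + 0.5 = 33.2% to 43.2%. In Scenario 2 the 12% dose is selected more often (37.6%) than the 20% dose (34.5%). In its favour, fewer patients are treated above the MTD: 3.6 against 4.2, 5.7 against 6.7, and 10.1 against 11.6 in Scenarios 2 to 4.

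**Beyond 12 patients.** Under the matching 9.1.1 rule, 25.6/32.7/29.5/18.0% of trials put more than 12 on one dose. The maximum is 21, reached in 1.4/2.8/3.6/2.4%.

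The printed cells confine λe to [1/7, 1/6) and λd to (2/9, 1/4]. Writing boundaries as escalate ≤ / de-escalate ≥:
- n = 15: 15λe lies in [2.14, 2.5) and 15λd in (3.33, 3.75], giving 2/4.
- n = 18: [2.57, 3) and (4, 4.5], giving 2/5.
- n = 21: [3, 3.5) and (4.67, 5.25], giving 3, and either 5 or 6. It is 5 if λd ≤ 5/21 = 0.2381, and 6 under the default 0.2385.

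Elimination needs only 9.1.2: Pr(p ≥ 0.20) is 0.973 at 6/15, 0.977 at 7/18 and 0.980 at 8/21, against 0.918, 0.932 and 0.944 with one DLT fewer.

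**The case against.** The strongest reply is that 9.2 is a summary. The operative algorithm is the numbered procedure in 9.1.1, Section 9.1.2 points to its table for conduct, and 9.1.3 uses the same loose wording as 9.2 above figures that came from the conditional rule. A design figure in 9.1.1 that cannot be seen here may restate the stop. Dose decisions also need principal investigator sign-off, with at least monthly calls (13.1), so a mismatch might be noticed. This makes the conditional rule the likelier intention. It does not make 9.2 agree with 9.1.1, and 9.2 is the section that claims the operating characteristics.

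Second, 9.1.1 read literally does not reproduce the table either: counting only the middle zone as a stay overshoots by 3.6 to 4.6 patients. That stands, and it is why *stay* needs a definition as well as a consistent stopping rule.

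Third, the effect is uneven. Correct selection moves by 1.0 point in Scenario 1 and 0.1 in Scenario 3, and the 9.2 rule exposes fewer patients above the MTD. This is right; the loss is in MTD selection, chiefly where the starting dose is already above target.

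Fourth, most missing boundaries can be derived. That is true at n = 15 and 18, but not for de-escalation at n = 21, and a study team should not have to derive boundaries during the trial.

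**Conclusion.** The concern holds and should be corrected. Sections 9.1.1 and 9.2 cannot both be followed, and the figures cited in 9.2 do not belong to the rule it states. Following 9.2 would cost about 3.6 points of correct MTD selection in Scenario 2 and 8.2 in Scenario 4, with little change in Scenarios 1 and 3 and somewhat less exposure above the MTD. Following 9.1.1 as simulated leaves about 18% to 33% of trials without a printed decision boundary at some point.

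The result rests on the default BOIN interval, which the plan does not state but which regenerates the whole printed table, and on a small pseudo-count in the isotonic step. Using 5 instead of 6 for de-escalation at n = 21 moves average N by about 0.02 and selection by about 0.1 points, so it does not affect the conclusion. For the same reason, the printed figures cannot show which value was used.

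**What to change.** Reconcile the sections to one rule before any dose reaches 12 patients.

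**If the conditional rule is intended**, which the printed table supports:
1. In 9.2, and for clarity in 9.1.3, add to the 12-patient stop: *and the next cohort would be assigned that same dose*.
2. In 9.1.1, define *stay* as the next cohort being assigned the same dose, including when no eligible higher or lower dose exists (highest dose, lowest dose, or next higher dose eliminated).
3. Extend the tables in 6.2 and 9.1.1 (escalate ≤ / de-escalate ≥ / eliminate ≥) to n = 15 (2/4/6), n = 18 (2/5/7) and n = 21 (3/6/8), and state the BOIN interval. The sponsor should confirm the de-escalation value at n = 21 from its own software output, since 5 is also compatible with the printed table.

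This costs a clause in two sections, one sentence, three columns and a statement of the interval. The printed operating characteristics stand and no simulation is needed.

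**If the unconditional rule is intended**, delete the condition from 9.1.1, re-run the simulation under that rule and replace the 9.1.3 table. The 12-patient decision tables then suffice.

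Either way, the maximum of 36, the elimination rule and the MTD estimator are unchanged.

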## 9. STATISTICAL CONSIDERATIONS

### 9.1 Study Design/Endpoints

This is a phase 1 trial to evaluate the safety and efficacy of various doses of entinostat combined with atezolizumab, carboplatin, and etoposide therapy for patients with treatment naïve ES-SCLC. Four dose levels of entinostat are detailed in Figure 1. The Bayesian optimal interval (BOIN) design will be used to find the maximum tolerated dose (MTD) based on safety (Liu and Yuan, 2015; Yuan et al., 2016). The target toxicity rate for the MTD is 20%. Due to overlapping hematologic toxicities between chemotherapy and entinostat, it may be difficult to separate attributions specifically to entinostat, particularly for thrombocytopenia events. Our DLT definitions will count these more extreme hematologic events at DLTs, although it is recognized that these occur in the setting of carboplatin and etoposide chemotherapy alone. Therefore, it is anticipated that a 20% DLT rate is a conservative estimate of the true DLTs directly related to entinostat. Furthermore, small cell lung cancer is an aggressive malignancy with poor overall survival. Additional toxicity is justified if there is potential for efficacy gains. Dose-limiting toxicities (DLT) will be determined by adverse events occurring during the first cycle of treatment. DLTs are defined in Section 6.2.

The primary endpoints of the study are:

- MTD of entinostat
- Grade 3/4 adverse event rate as defined by CTCAE v5.0
- Number of cycles received of the combination of entinostat, atezolizumab, carboplatin, and etoposide (maximum = 4)

The secondary endpoint of the study is:

- 9-month PFS rate, defined as the proportion of patients alive and without disease progression after 9 months from study enrollment

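### Section 9.2 calls the rate of selecting the target dose high, but the Section 9.1.3 table it cites shows 38–52%, and that table reproduces under the stopping rule in 9.1.1 but not the one worded in 9.2

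*Combined protocol and SAP*

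**What the plan says.** Section 9.1 fixes the target: "The target toxicity rate for the MTD is 20" per cent. In each simulated scenario the target dose is therefore the level whose true DLT rate is 0.20. Section 9.1.3 tabulates, among other things, "the percentage of simulated trials selecting each dose level", from 10,000 simulated trials per scenario.

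Section 9.2 states that "The maximum sample size is 36 participants" and then draws on that table: "the sample size results in a high rate of simulated trials identifying the target dose level as the MTD across multiple dose-toxicity scenarios". It presents this as showing that the design can achieve the primary aim of finding the MTD. It gives no threshold for *high* and no comparator.

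The plan words the early stop in two ways. In Section 9.1.1 the stop is conditional: "the number of participants treated at the current dose reaches 12 and the decision according to the table below is to stay", meaning no change of dose level. Section 9.2 says "the trial will stop accruing participants once 12 participants have been treated on a single dose level", with no condition on the decision. The text introducing the table in 9.1.3 also describes the stop without that condition.

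**The concern.** The sentence in 9.2 is the plan's only quantitative support for the sample size, and the MTD is a primary objective. A reader who takes *high* at face value will expect the trial usually to land on the right dose. The cited table shows that in three of four scenarios it lands elsewhere, or selects nothing, more often than not.

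The table's figures also depend on when accrual stops. If the rule printed in 9.2 is not the rule that was simulated, the table does not describe the trial that 9.2 describes.

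**Working it through.** **Inputs.** Target 20% (9.1). "Participants will be enrolled and treated in cohorts of size 3" and "Participants in the first cohort are treated at dose level 1" (9.1.1), with four levels: -1, 1, 2, 3. Maximum 36 (9.2). Elimination when the posterior probability that the DLT rate is at least 0.20 exceeds 0.95, with a uniform prior and at least 3 treated (9.1.2). MTD chosen by isotonic regression (9.1.1). True rates and selection percentages from 9.1.3.

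**Step 1: read the table against the target.** Below, target and above are sums of the printed selection percentages; missed = 100 − target.

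| Scenario | Target level | Below | Target | Above | Missed |
|---|---|---|---|---|---|
| 1 | 3 | 2.89 + 15.7 + 32.7 = 51.29 | 48.64 | none exists | 51.36 |
| 2 | 2 | 7.41 + 36.52 = 43.93 | 38.13 | 17.56 | 61.87 |
| 3 | 1 | 29.55 | 44.92 | 18.6 + 3.43 = 22.03 | 55.08 |
| 4 | -1 | none exists | 51.73 | 27.54 + 5.17 + 0.5 = 33.21 | 48.27 |

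The unweighted mean of correct selection is (48.64 + 38.13 + 44.92 + 51.73)/4 = 45.9%. In Scenario 4 the missed share includes the 15.1% of trials stopped early for safety.

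The target against its nearest single rival is 48.64 v 32.7, 38.13 v 36.52, 44.92 v 29.55 and 51.73 v 27.54. It leads in all four, but by only 1.61 points in Scenario 2.

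The adjacent dose, at a true rate of 28%, supplies 17.56 of 17.56, 18.6 of 22.03 and 27.54 of 33.21 of the above-target points in Scenarios 2 to 4.

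**Step 2: reproduce the table.** The documents do not state the BOIN interval limits, so the usual 0.6 and 1.4 times target (0.12 and 0.28) are assumed:

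- Escalation boundary: log(0.88/0.80) / log[0.20 × 0.88/(0.12 × 0.80)] = 0.157.
- De-escalation boundary: log(0.80/0.72) / log[0.28 × 0.80/(0.20 × 0.72)] = 0.238.

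These boundaries and the 0.95 elimination rule return the plan's decision table exactly for 1 to 12 patients. With 10,000 simulated trials per scenario (Monte Carlo standard error at most √(0.5 × 0.5/10,000) = 0.5 points):

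| | Sc. 1 | Sc. 2 | Sc. 3 | Sc. 4 |
|---|---|---|---|---|
| Printed: target % | 48.64 | 38.13 | 44.92 | 51.73 |
| 9.1.1 rule: target % | 48.9 | 38.4 | 44.4 | 51.6 |
| 9.2 wording: target % | 47.5 | 35.2 | 45.1 | 43.0 |
| Printed: above % | 0 | 17.56 | 22.03 | 33.21 |
| 9.1.1 rule: above % | 0 | 17.4 | 21.9 | 33.8 |
| 9.2 wording: above % | 0 | 19.5 | 25.6 | 43.7 |
| Printed: average N | 23.7 | 23.7 | 22.3 | 19.4 |
| 9.1.1 rule: average N | 23.6 | 23.7 | 22.1 | 19.6 |
| 9.2 wording: average N | 20.5 | 19.8 | 18.3 | 16.6 |

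The 9.1.1 rule is run as: stop when 12 have been treated at the current dose and the next cohort would stay there, including when the dose cannot move because it is the highest or lowest. It matches on every line. The 9.2 wording fails most clearly on average N and on Scenario 4. Under it the target is no longer the leading dose in Scenario 2 (35.2% v 37.3% for the level below). Repeat runs of the 9.2 wording gave about 34–48% correct and about 43–44% above target at worst.

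**The case against.** The strongest reply has five parts.

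- *No figure is wrong and nothing is hidden.* True. The full table stands in the section just before 9.2. A reader might infer an arithmetic error or a faulty simulation; the reproduction rules that out for the 9.1.1 rule.
- *The target is the modal choice everywhere.* True, and the corrected sentence should say so. Pooling the lower doses makes them outweigh the target in Scenarios 1 and 2, but no single lower dose does. Being the leading dose is still a weaker property than a high rate.
- *One half is not a standard set in the plan, and may be unattainable.* This stands as far as it goes. A benchmark that knows each patient's outcome at every dose selects the target in about 67, 41, 40 and 66% of trials with 24 patients, and about 75, 49, 48 and 70% with 36. In Scenarios 2 and 3 the design is close to, or above, the 24-patient figure; in Scenarios 1 and 4 it falls short. That is an argument for calling 38–52% acceptable, which the plan could make with the figures. It does not make the rate high.
- *The 33% is a worst case.* Also true. In Scenario 4 the lowest level is the target and the trial starts one level above it. Doses with true rates above 28% are selected in only 3.43% (Scenario 3) and 5.17 + 0.5 = 5.67% (Scenario 4). A dose with a true rate of 12–28% is selected in 81.3, 92.2, 93.1 and 79.3% of trials.
- *The recommended phase 2 dose may be set below the MTD after safety review (9.1.1).* It may, but that step is discretionary, is not described as part of the simulations, and does not correct an MTD set too low.

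**Conclusion.** The concern holds as a misdescribed operating characteristic. Section 9.2 claims a property that its cited table does not show: correct selection is 38–52%, the target is missed in more than half of trials in three of four scenarios, and an above-target dose is chosen in 0–33%.

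A reader might go further and conclude that the design is unsound or the sample too small. The documents do not support that. The table is reproducible, most above-target selections are one level too high, and running all 36 patients with no stop at 12 gives only about 56, 43, 46 and 50% correct, so filling the existing cap would not by itself produce a clearly high rate.

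The figures rest on the four printed scenarios and on the 9.1.1 stopping rule. The reproduction also rests on the assumed interval limits, which return the plan's decision table exactly. The unconditional wording in 9.2 describes a trial with different performance, so the figures cannot be placed beside it without saying which rule they belong to.

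**What to change.** In 9.2, replace the *high rate* wording with the figures, for example: *the target dose is the most frequently selected dose in each scenario, chosen in 38–52% of simulated trials; a dose with a true DLT rate above 20% is chosen in 0–33%*. If the sponsor regards this as acceptable, a sentence should say why.

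State that these figures apply to the 9.1.1 rule: 12 treated at the current dose and the decision is to stay. Reconcile the unconditional stop-at-12 wording in 9.2 and 9.1.3 with 9.1.1. If the unconditional rule is the intended one, the table must be simulated again under it before any figures are quoted.

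The cost is a few sentences and a less favourable stated performance. Dose allocation and MTD selection need not change.
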